7.4 Statistical model selection procedure

We will follow the model selection steps outlined in Masyn (2013):

- Initial model is fitted with a single class as a reference. Recording the log-likelihood value
 (LL); number of parameters; Akaike's Information Criterion (AIC); Bayesian Information
 Criterion (BIC); Consistent Akaike's Information Criterion (CAIC), and approximate weight of
 evidence (AWE).
- ii. Next, fit a set of K-class models, where K increases by 1 for each new LCA model. The maximum number of LCA models fitted can be determined when the Kth model is not identified. We propose to fit a maximum K = 6 class model initially. A higher number of "service types" would need to be theoretically justified before fitting larger K models. In addition to the fit indices, likelihood-based tests (LMR and BLRT) will be recorded between all K and K-1 models and p-values reported accordingly (significance level, $\alpha = 0.05$).
- iii. All models fit indices and likelihood-based tests results will be reported in a table for comparison. Lower fit indices indicate improved fit. In addition, the fit indices will be plotted against their respective K-class index, known as an elbow plot, to aid interpretation of the correct LCA model. Interpretation of the most parsimonious model involves choosing the point at which the fit visibly changes, i.e. the "elbow" observed indicating a significant reduction in the differences in fit indices.

iv. Models will be selected based on all evidence from the above measures and the selected Kclass model will be reported. A path diagram of the selected LCA model and corresponding class profile plot will be included as part of the results to further aid interpretation.

A brief note on model validation. Split-half validation is not possible as the available sample of data is constrained by the number of services in the UK, so adequate sample size for each half of the data would be insufficient to achieve satisfactory model fit. Therefore, will only report the models based on the complete sample.

7.5 Class interpretation and designation of service model labels

The statistical identification of potential typology of service models will be used as part of the evidence base in combination with typologies identified by the qualitative analyses and expert interpretation to decide on the final typology. The face validity of these classes and the classification of services will be discussed, and decisions around further groupings (either collapsing or expanding classes) will be documented leading to a final description of current service models for children with LD and BtC. As noted by Weller et al. (2020), adding representative class labels should be with reference to theoretical justifications. Statistically-derived classes will be identified and the contributing variables summarised for each class to provide an holistic description of the potential service model.

When attaching class labels to statistical groupings, data describing the context for the services (i.e. additional information from the interview and available demographics details), not used in the LCA, will also be used to enrich the descriptions of each potential service model.

7.6 Assumption violation/Model non-convergence

LCA models may require tuning after initial model fit to ensure convergence. These models can be sensitive to local maxima if weakly identified, indicating that the log-likelihood surface is relatively flat and may contain multiple potential solutions causing non-convergence or that a solution is not replicated. Often this can be an indicator that the model does not support the data and too many classes are trying to be estimated. In this scenario, the model's complexity will be reduced or investigation of variables that may be problematic will be carried out and the models potentially adjusted as a result.

Appendix

Table A shows the variables included into the analysis and any data wrangling/cleaning procedures used.

Variable	Variable type (No. of categories)	Description (original survey question)	Variable manipulation from original survey questions (recategorized or transformed)
Q1	Continuous	How long has the service been in place? Years Months	Variable has been transformed to a single scale in months only, rather than two variables (years, months).
Q3/4	Categorical (3)	Q3 Does the service stand-alone or is it part of/a sub-team of another service? • Stand-alone service • Part of another service Q4 Please describe what other service or sub-team your service is part of (only display if answer 'part of another service' to Q3) Open ended	Information from these two questions has been combined and categorised by the research team: 1) Stand-alone service 2) A larger children's service A larger children's mental health service 3) A larger child LD/autism service OR in a LD team covering a wider age range than just children
Q5/6	Multiple dichotomous (5)	Q5 Who commissions the service? If this service is jointly commissioned, please select all that apply. If there is more than one commissioner, you will then be asked to explain the rough proportions of share in funding.	Convert to multiple items: 1) single vs multiple commissioner 2) dichotomous items -

		 NHS specialist commissioning Local authority: Education Local authority: Social care Private organization or company Voluntary organization or charity Private individual Clinical commissioning group (CCG) Transforming care partnership (TCP) Integrated care system (ICS) Sustainable transformation partnership (STP) Other (text from 'other' answer in Q5): Q6 You selected more than one commissioner. Please tell us the approximate percentage of funding that comes from each of the options you selected? (only display if 2 or more options selected in Q5. Only options selected in Q5 displayed)	These items capture the types of commissioner: i. Any Local authority (including social care or education or both) (yes/no) ii. Any Clinical Commissioning Group (CCG) (yes/no) iii. Any Transforming Care Partnership (TCP)/Integrated Care System (ICS)/ Provider collaborative(yes/no) iv. Any NHS England specialist commissioning (yes/no)
Q8	Dichotomous	What are the ages of the children and young people with behaviours that challenge who	This variable was reclassified into the following two categories: 1) 0-25+ (all age) 2) 12 – 25+ (adolescent and young adult only)

Q9	Categorical (2)	can access the service? Please select all that apply • 0-4 years • 5-11 years • 12-15 years • 16-19 years • 20-25 years • 25+ years At what age do children and young people with behaviours that challenge transition out of the service to a service for individuals who are older? • There is no adult service to which they transition • They stay with the same service/team • 16 years of age • 17 years of age • 18 years of age • 19 years of age • 20 years of age • 21 years of age • 22 years of age • 23 years of age • 24 years of age • 25 years of age • 26+ years of age	This variable was reclassified into the following four categories: 1) 16 – 18 years of age OR "There is no adult service" 2) 19-26+ years of age OR "stay within the same service" This variable was reclassified
Q11	Categorical (2)	What groups of children and young people with behaviours that challenge is the service for (in terms of inclusion criteria for	into the following three categories: 1) Learning (intellectual) disabilities AND/OR Autism only

		the service)? Please select all that apply Children and young people with learning (intellectual) disabilities Children with global developmental delay Autistic children and young people who do not have a learning (intellectual disability) Children and young people who both have learning (intellectual) disabilities and who are also autistic Other disabled children and young people Non-disabled children and young people Non-disabled children and young people Other children and young people Other children and young people with particular "diagnoses" (please describe if selected):	2) Learning (intellectual) disabilities and Autism and Other
Q12	Dichotomous	Is the service only for children and young people with behaviours that challenge (even if they also have other support needs)? Yes No	Unchanged from raw survey data
Q14	Dichotomous	Who can refer children and young people with behaviours	Information from this question has been re-categorised by the research team into a dichotomous variable:

		that challenge into your service? Please select all that apply General Practitioners/Primary Care Self-referrals/Referral directly from the child's carer School – mainstream School - special Child and Adolescent Mental Health Services (CAMHS) Other health professionals Pre-schools Social services Third sector organisations Paediatricians Other (please describe)	"Does the service accept self- referrals as well as professional referrals?" 1) No, Professional referral only 2) Yes, Professional or Self- referral
Q18	Continuous	Approximately what is the current total active caseload for the service of children and young people with behaviours that challenge? Numerical	Initially included into the LCA analysis without manipulation, but may require a transformation if problematic in initial model runs.
Q19	Categorical (4)	For each of the following professional groups, please indicate how many staff in the service are from this background. If nobody of this profession works in the service, please answer 'O'. Please categorise staff by main role. There will be a follow up question asking about approximate full time equivalent for those professional groups	This variable was reclassified a categorical variable indicating profiles of skills mixes in each service: 1) Mostly psychologists (clinical and/or assistant) (>50%); 2) Mostly Learning Disability nurses (>50%);

		more staff of in your service. If there are staff in your service from other backgrounds, please indicate these in the 'other care staff' option. - Assistant Psychologist - Assistant Social Worker - Clinical Psychologist - Dietician - General Nurse - Health Care Assistant - Learning Disability Nurse - Mental Health Nurse - Occupational Therapist - Physiotherapist - Psychiatrist (e.g., Consultant Psychiatrist, Staff Grade Doctor) - Qualified teacher - Speech and Language Therapist - Social worker - Support worker - Other (please describe)	or support worker (>50%, other includes behavioural analyst, practitioners, outreach workers) 4) Mixed (mixture of professional groups with no overall majority, either 50:50, or lots of smaller proportions for more professions)
Q21/22	Categorical (x2)	Q21 Do any of the staff in the service have any specialist training and qualifications (with some certification such as University or other training provider awards/credits) in behaviours that challenge beyond their professional training? For example, in positive behaviour support? Yes No	These variables will be reconfigured into three categorical variables indicating their intensity of expertise on each of the three domains from Q22: • Positive behaviour support course Categories for each variable will be as follows:

		Q22 How many staff in the service have had specialist training and qualifications in behaviours that challenge beyond their professional training? Please enter total number of staff for all that apply. If no staff have these qualifications please enter 0 (zero). (only displayed if 'yes' selected in Q21) Positive behaviour support course Challenging behaviour course Other (please describe)	1) No staff with specialist training or less than 50% have specialist training 2) 50-75% of staff have specialist training 3) >75% have specialist training These variables will be reconfigured into three categorical variables indicating their intensity of expertise on each of the three domains from Q22: • Challenging behaviour course Categories for each variable will be as follows: 1) No staff with specialist training or less than 50% have specialist training 2) >50% of staff have specialist training
Q24	Categorical (3)	What intervention approaches does your service typically carry out that involve directly delivering interventions to children and young people with	Information from this question has been re-categorised by the research team into a four- category variable: 1) Behavioural and skills development (Behavioural interventions that concern behaviours that challenge, Writing a behaviour support plan, Delivering a multi-

		behaviours that challenge? Please select all that apply. Reducing challenging behaviour using medication Behavioural interventions that concern behaviours that challenge Writing a behaviour support plan Delivering a multi-element behaviour support plan Increasing communication skills Increasing other adaptive skills (e.g., social or independence skills) Psychological therapies for mental health problems Physical health interventions Pharmacological interventions for mental health problems Psychological / pharmacological interventions for poor sleep Other therapies (e.g., art therapy, music therapy, play therapy) Sensory interventions Other (please describe)	element behaviour support plan, Increasing communication skills, Increasing other adaptive skills (e.g., social or independence skills)) 2) Most categories of interventions 3) Other categories (excluding those from (1))
Q31	Dichotomous	•	Information from this question has been re-categorised by the research team into a dichotomous variable:

and their families? Please select all that apply The child and/or young person's behaviours that challenge The child and/or young person's quality of life The child and/or young person's skills, such as communication skills, social skills, independence skills The child and/or young person's mental health (e.g., anxiety, mood/depression) Family carer well-being and quality of life (including quality of life of the family as a whole) Family carer experience and satisfaction with services/support received Other (please describe)	1)	Child and parent family measures
	2)

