14.1 Progression criteria for Stage 2 of the research

The following progression criteria using a Traffic Light model will be used to inform a decision to move on from the current project to research evaluating outcomes and costs of service models (Stage 2 of the research):

1. TCP contacts – interviews completed

Green – Initial interviews with a lead from 75% or more of TCPs in England are completed

Amber - Initial interviews with a lead from 60% or more of TCPs in England are completed, but larger TCPs have mainly been included

Red - Initial interviews with a lead from fewer than 60% of TCPs in England are completed

2. Leads from identified services – Data collected

Green – Data collected from 70% or more of services identified at the TCP interview step

Amber - Data collected from 60% or more of services identified at the TCP interview step, but there has been a higher level of engagement from services other than LD CAMHS (that we anticipate will be a common service model)

Red - Data collected from fewer than 60% of services identified at the TCP interview step

3. Service models identified from the Latent Class Analysis and Stakeholder consultation

Green – At least 4 service models are identified to take forward to Stage 2

Amber – 2 or 3 services models are identified to take forward to Stage 2, and there are sufficient numbers of these services to be included in Stage 2

Red – No distinct service models are identified

A recommendation to progress will be made if green criteria are met. Progression will also be recommended if green criteria are missed but amber criteria are met; and the recommendations made will then include consideration of the implications for the proposed second stage of the research (observational study).

15 Data Management

Source data will be an electronic record in Qualtrics, downloaded at least weekly into Microsoft Excel. Qualtrics and Excel will only contain a unique Service Identification Number (SIN) per service. No other identifiable information will be recorded. Records of consent will contain participant and service names, and contact forms will contain service manager/clinical lead contact details (email and telephone number). Consent and contact details, and data from services will be stored on a University of Warwick secure drive that can be accessed by the research team only.

Identifiable data will be encrypted and stored separately from non-identifiable data.

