5.2 Variables and selection procedure

All variables from the survey will not necessarily be included into the proposed analysis as they may not be informative to the model but will be used as part of the description of classes and in further discussion around the identification of services. Some variables in their current format will require some pre-processing to be used in the main analysis. Table A, found in Appendix, shows all variables included into the analysis and briefly outlines any procedures used to reformat the variables for inclusion into the analysis.

6 Statistical considerations

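### The single/multiple commissioner item in the latent class model is partly fixed by the four commissioner-type items entered beside it, so local dependence is built in and extra classes are favoured

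*SAP*

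**What the plan says.** SAP section 5.2 says that Table A "shows all variables included into the analysis". In that table, the row for Q5/6 reads "1) single vs multiple commissioner 2) dichotomous items". The dichotomous items are introduced with "These items capture the types of commissioner" and are four yes/no indicators: any local authority, any CCG, any TCP/ICS/provider collaborative, and any NHS England specialist commissioning. With the single/multiple item, that makes five indicators from one tick-all-that-apply question.

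The SAP gives no rule for deriving the single/multiple item. The nearest thing is the display condition for Q6, which is shown when two or more Q5 options are ticked.

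For the number of classes, SAP section 7.4 starts with a maximum of six, records AIC, BIC, CAIC and AWE, and adds that "likelihood-based tests (LMR and BLRT) will be recorded between all K and K-1 models", at a 5% level. An elbow plot is also used and the evidence is weighed together. Protocol section 14 names AIC as the index. SAP section 7.5 then combines the statistical classes with qualitative typologies and expert interpretation.

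Protocol section 14.1 sets the green criterion as "At least 4 service models are identified to take forward to Stage 2"; two or three models is amber. The Stage 2 protocol (Appendix 2) reports five models and takes 15 services, three per class, from 161.

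**The concern.** Latent class analysis attributes all association between indicators to class membership. Where two indicators are tied by their definitions, the association remains within every class, and the model can absorb it only by adding or distorting classes. Here a service with two commissioner types marked yes cannot be single, whatever its service model.

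SAP section 7.6 mentions assumption violation in its heading, but its text deals only with non-convergence and solutions that fail to replicate. A logically tied indicator need not trigger either. No bivariate residual check is planned, and SAP section 7.4 rules out split-half validation.

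At stake is the class count and the assignment of services to classes. The count bears on the amber/green boundary (three against four models), and the classes supply the strata from which Stage 2 draws its services.

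**Working it through.** **1. How far the four type items determine the single/multiple item.** Q5 has 11 options, giving 2^11 − 1 = 2,047 non-empty selections. Each was mapped to the Table A items, with multiple taken as two or more options ticked (the Q6 display condition).

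- The four type items have 2^4 = 16 patterns.
- Patterns with two or more types marked yes: 6 + 4 + 1 = 11. All 11 force multiple.
- Patterns with none or exactly one yes: 1 + 4 = 5. Each allows either value. CCG alone is single; CCG plus a charity has the same four-item pattern but is multiple.
- Possible five-item cells: 11 + (2 × 5) = 21 of 32. The other 11 are structural zeros.

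Five cells stay open in both directions for two reasons. Private, voluntary, private individual, other and (as written) STP have no type item. Local authority education and social care are two options merged into one item, as are TCP and ICS.

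**2. What local independence then requires.** For any two types A and B, the combination (A yes, B yes, single) is impossible. Within each class c this means

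P(A|c) × P(B|c) × P(single|c) = 0.

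So each class must be either wholly multiple or have at most one type with non-zero probability. If each of the four types occurs as a sole commissioner and some services have two types, an exact fit needs at least 4 + 1 = 5 classes from the coding alone. This needs no assumed rates, but it concerns exact fit. It does not say what a criterion would choose in a finite sample.

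**3. Size, by simulation.** The plan's own figure, about 90% power for three classes over two with 150 services, cannot be recomputed: the documents give no item probabilities, class sizes or number of items for it. The point does not rest on it.

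The documents give no commissioner frequencies, so these are assumptions. Two sets of rates were used, giving multiple 27–48%, local authority 13–35%, CCG 82–95%, TCP/ICS 7–14% and NHS England 4–10%. Twelve other binary items were added, independent within class. One-class scenarios had 60 runs each, the bootstrap test 25 runs with 39 bootstraps, and three-class scenarios 40 runs each.

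| Truth | Result | With item | Without |
|---|---|---|---|
| One class, N=150 | BIC chooses more than one | 28–43% | 0% |
| One class, N=161 | BIC chooses more than one | 30–67% | 0% |
| One class, N=150 and 161 | AIC chooses more than one | 100% | 52–65% |
| One class, N=161 | BLRT rejects one class | 100% | 8–16% |
| Three classes, N=161 | AIC chooses more than three | 100% | 57–60% |
| Three classes, N=161 | BIC chooses exactly three | 100% | 100% |

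Two further sets under the same Q5 rule at N=161, also with assumed rates:

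- 30 runs. One true class: BIC added a class in 77% with the item against 0% without. Three true classes: the median 4-v-3 likelihood ratio was 59 against 34, AIC chose more than three in 100% against 70%, and BIC did so in 0% either way.
- 40 runs, with the item replaced by an independent item of equal prevalence, so that the number of parameters is the same. Three true classes: the 4-v-3 likelihood ratio exceeded the comparator's 95th centile in 98% of runs (5% expected; medians 67 against 45), AIC preferred four to three in 100% against 62%, and BIC in 0% of both. One true class: the 2-v-1 ratio exceeded that centile in 100%, and BIC added a class in 48% against 0%.

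**The case against.** A reader might infer that the single/multiple item is simply computed from the other four. The documents do not support that: the SAP states no such rule, and 5 of the 16 type patterns leave the item open. The distinction affects the size. If the item were a strict function of the four, BIC would choose more than one class in 98–100% of one-class runs; under the Q5 rule the range across the simulations is 28–77%.

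A reader might also infer that a spurious class must result, or that one of the five reported models is an artefact. Neither follows. BIC did not move when three real classes were well separated. AIC over-selects often even without the item, so its excess is only partly due to this coding. The SAP does not choose on AIC alone.

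Nor does the statistical count by itself decide progression. SAP section 6.1 says the latent class findings are not confirmatory in their own right, SAP section 7.5 allows classes to be collapsed or expanded, and criterion 3 in protocol section 14.1 counts models after stakeholder consultation, with progression still recommended under amber.

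All of that stands. It does not remove the point. Expert review judges whether a class looks plausible, and a class of jointly commissioned services could look plausible whether it reflects a service model or the coding. The likelihood ratio tests and AIC, which are distorted, are among the listed criteria, and the five items are entered together as written.

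**Conclusion.** The specification is wrong as written. Five indicators from one question are entered together, and 11 of their 32 joint patterns are impossible by definition, so local independence fails by coding. That part is certain from Table A if multiple means more than one commissioner.

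The consequence is a pull towards extra classes, clearest on AIC and the likelihood ratio tests. With three true classes at N=161, AIC went above three in 100% of runs with the item against 57–70% without it, and the 4-v-3 likelihood ratio was inflated in 98% of runs against a matched independent item. BIC was robust in that setting and vulnerable mainly when there was no real class structure.

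These sizes rest on assumed commissioner rates, mainly binary or categorical companion items (Table A also has continuous Q1 and Q18), well-separated classes in the three-class case, and modest numbers of runs. LMR was not simulated; its exposure is inferred from the likelihood ratio on which it is based.

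This is a correctable modelling error that should be fixed, not one that invalidates the Stage 1 typology.

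**What to change.** 1. State in Table A the rule that derives the single/multiple item: whether it counts Q5 options or the four grouped types, and how merged and unlisted commissioners are handled.
2. Take the item out of the latent class indicators, keep the four type items, and use it to describe the classes. At the least, refit without it.
3. Report whether the number of classes and the assignment of services change, with all fit indices and tests shown both ways.
4. Add a check of bivariate residuals for the remaining related pairs, such as Q8 with Q9 (age range and transition age) and the two Q22 training items.

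The cost is a change to one row of Table A, a refit and a short sensitivity table. Some information leaves the indicators: co-commissioning by private, voluntary or other bodies, and joint local authority education and social care funding, would be reported only descriptively. Protocol section 11 (Step 2) lists the funding/commissioning model as a key dimension, so that description should be given in full. Stage 2 is already built on five models (5 × 3 = 15 services). If assignments change on refitting, the report should say which selected services are affected and how this bears on the comparison between models.

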4	(Non substantial)	V1.4	9.11.2021	
Edited the methodology summary in Section 2 to include additional methods of identifying and recruiting services. Amendments to other protocol sections have been made to reflect these additional methods: Section 3 (3.1 - study flow diagram), Section 6 (Phase 1 – identification of services), Section 9 (9.2), Section 11 (Step 3. Identification of other local services).

[figure not shown]
2 Synopsis

Title	Mapping Services for Children with Learning Disabilities and Behaviours that Challenge
Acronym	MELD
Funder and ref.	NIHR 129577
Study design	Survey to identify distinct service models in England for children with learning disability and behaviours that challenge
Study participants	Staff in community services for children with a learning disability and behaviours that challenge
Planned sample size	48 leads for Transforming Care Partnerships in England (or successor organisations) Two staff from each of approximately 200 community services for children with learning disability and behaviours that challenge (400 Staff)
Inclusion criteria	The inclusion criteria for services are: 
 1. Geographically located in, and at least partially drawing referrals from, England 2. Community-based service 3. NHS, local authority or other (e.g., private, charity) service commissioned by a CCG/local authority/STP/ICS, or a service where individual places are purchased by CCG/local authority or other commissioners 4. Providing supports for children with LD 0-17 years of age with learning disabilities and behaviours that challenge or providing supports to this group of children as a clearly distinct care pathway (whilst also providing other services). Services will not be excluded if they also provide services to individuals 18+ years of age as well as within the 0-17 age range.
Exclusion criteria	Exclusion criteria are: 
 • Inpatient service • Service commissioned by non-CCG or local authority commissioner (e.g., solely a special school service)

[figure not shown]
	
 • Service that is not yet operational (i.e., has received no referrals at the time of data collection)
Planned study period	12 months
Primary objective	To map community services for children with learning disability (LD) and behaviours that challenge (BtC) in England, to describe distinct service models

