We will make contact with all 48 Transforming Care Partnerships (TCPs) across England, or (where these have recently evolved) with relevant Sustainable Transformation Partnerships (STPs) or Integrated Care Systems (ICS). TCPs have been an organisational structure associated with the Transforming Care Policy Programme and link together commissioners and services in a region of England. Each TCP has a named lead who will be contacted by a researcher to carry out an initial telephone interview to identify in each TCP area the health/care services to which children with LD and BtC would be referred for community based support (not inpatient only services). The NHS England and Improvement Long Term Plan Implementation Framework requires that where TCPs have been embedded within STPs or ICS, that there remains a named senior responsible officer for LD and Autism. Thus, we can still identify and contact these key individuals. We will also identify services via local authority websites, recruited service providers giving details of other services to contact, online recruitment via social media/website, or via expressions of interest. Additional recruitment options will be to contact R&D departments directly; contacting regional and national NHS England contacts; or using a Freedom-of-Information request (FOI). “Children” are defined as 0-17 years of age for the purposes of the current research, but services will not be excluded if they

provide support to young people beyond this age range. Our NHS England and Improvement child LD policy team partner ([name]) already has excellent and regular links with TCP/STP/ICS contacts across England. Thus, we anticipate a high response rate. At the end of Phase 1, we will have more detailed information about the likely total population of services for children with LD and BtC in England and some initial information about basic characteristics of those services (e.g., whether services are NHS, Local Authority, other).

Phase 2 - Selection of services/Sample size

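### SAP Table A, Q5/6: the TCP/ICS commissioner item leaves out STP, so as written a service commissioned by an STP can be scored no

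*SAP*

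**What the plan says.** Table A in the SAP Appendix lists the LCA variables and their recodes. Q5 asks who commissions the service and lets respondents tick all that apply. One option is "Sustainable transformation partnership (STP"), listed separately from TCP, ICS and CCG.

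The Q5/6 row is typed as "Multiple dichotomous (5"): one single-versus-multiple commissioner item and four yes/no items for type of commissioner. These are (i) any local authority, (ii) any CCG, (iii) "Any Transforming Care Partnership (TCP)/Integrated Care System (ICS)/ Provider collaborative(yes/no") and (iv) any NHS England specialist commissioning. STP appears in none of the four. Table A gives no residual category, no missing-value rule and no reason for the omission.

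Elsewhere STP stands beside the bodies named in item iii:
- The inclusion criteria in the Stage 1 protocol synopsis, repeated in the SAP synopsis, admit a service "commissioned by a CCG/local authority/STP/ICS".
- Stage 1 protocol Section 6, Phase 1, has the team contact TCPs or, where these have evolved, make contact "with relevant Sustainable Transformation Partnerships (STPs) or Integrated Care Systems (ICS"). It also refers to the case "where TCPs have been embedded within STPs or ICS".
- Stage 1 protocol Section 6, Phase 2, and SAP Section 6.1 count expected services per combined TCP/STP/ICS area.

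**The concern.** Item iii appears meant to capture commissioning at the regional partnership level. If STP is left out, two services commissioned at that level get different codes only because one respondent ticked STP and the other ticked ICS or TCP. The LCA would then treat a difference of name as a difference of commissioning.

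The commissioner items help define the service models carried into Stage 2. There, service model is the exposure in the regression (Stage 2 protocol, Section 14), and three services per class are to be selected from 161. One service placed in the wrong class would be a third of that class's sites.

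**Working it through.** **Item count.** 1 single/multiple item + 4 type items = 5, which matches the count in Table A. The five are therefore fully accounted for, and none is a separate STP item.

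**Rules applied as written.** Each row is a possible Q5 answer. The last column shows item iii with STP added.

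| Q5 ticks | Single/multiple | i LA | ii CCG | iii as written | iv NHSE | iii with STP |
|---|---|---|---|---|---|---|
| TCP only | single | no | no | yes | no | yes |
| ICS only | single | no | no | yes | no | yes |
| STP only | single | no | no | **no** | no | **yes** |
| Charity only | single | no | no | no | no | no |
| Private organisation only | single | no | no | no | no | no |
| CCG + ICS | multiple | no | yes | yes | no | yes |
| CCG + STP | multiple | no | yes | **no** | no | **yes** |
| STP + ICS | multiple | no | no | yes | no | yes |

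Three things follow.
1. An STP-only service matches a charity-only or private-only service on all five items and differs from an ICS-only or TCP-only service on item iii.
2. The item iii problem is wider than STP-only services. It reaches any service that ticks STP without TCP, ICS or a provider collaborative, such as CCG + STP.
3. A service that ticks STP together with TCP or ICS is unaffected.

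Adding STP leaves the item count at 5.

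**How many services.** The documents give no Q5 frequencies. Let s be the share of the 161 Stage 1 services that ticked STP, and f the fraction of those already yes on item iii. Then the number whose code changes is 161 × s × (1 − f). Both s and f are assumptions, and the values below are illustrations, not estimates.
- s = 2%, f = 0: 161 × 0.02 = 3.2, about 3 services.
- s = 10%, f = 0: 161 × 0.10 = 16.1, about 16 services.
- s = 10%, f = 0.5: 161 × 0.10 × 0.5 = 8.05, about 8 services.
- s = 0 or f = 1: none.

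**Weight in the model.** The readable rows of Table A give 18 indicators: five from Q5/6, two from Q21/22, and one each from Q1, Q3/4, Q8, Q9, Q11, Q12, Q14, Q18, Q19, Q24 and Q31 (5 + 2 + 11 = 18). Item iii is one of these.

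**The case against.** The strongest reply is that the SAP nowhere says STP is scored no; it is silent. Item iii also names provider collaboratives, which are not a Q5 tick-box, so the team evidently classified some answers by judgement and may have placed STP under item iii in practice. That stands as a statement about the data: the actual coding cannot be seen. It does not rescue the written rule, because a yes/no item that names its members gives no for a body it does not name.

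Second, Q5 allows several ticks, so the all-no profile needs an STP-only answer. Sections 8.1 and 8.2 of the Stage 1 protocol, read literally, require commissioning or purchase of places by a CCG or local authority, which would exclude an STP-only service and the charity-only comparator. The synopsis is wider and admits STP and ICS. This narrows the all-no case but not the item iii problem: a CCG + STP service is eligible on either reading and is still scored no.

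Third, the LCA is not the last word. Stage 1 protocol Section 14 and SAP Section 7.5 have experts and stakeholders discuss the classification and collapse or expand classes, which limits the harm from one item.

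A reader might go further and conclude that Q9 is miscoded too, because "There is no adult service to which they transition" carries no age yet shares a category with leaving at 16 to 18. The documents do not support calling that an error. The category is a declared either/or. Services that keep people have their own answer, coded with 19 and over. Having no adult service can plausibly mean that support ends around 18 with nothing onward. Nothing shows that any service seeing people to 25 or beyond chose that answer. Placing Q9 answers by the Q8 age bands would be a debatable choice, not a correction. What remains is a stated grouping with no stated reason; the SAP amendment log cites low cell frequencies only for Q3/4, Q11 and Q22.

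**Conclusion.** The point holds for Q5/6 only, as a minor one. Item iii omits a commissioner that Q5 offers and that both documents group with TCP and ICS. Applied as written, it scores no for any service that ticks STP without one of the three named bodies.

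This rests on reading Table A literally. A reader might infer that services were in fact miscoded or put in the wrong class. The documents show neither: they give no answer frequencies, no coded data and no class assignments that depend on this item. The number affected may be small or zero, and the illustrative counts above only restate their assumptions.

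**What to change.** Reword item iii to: Any TCP/STP/ICS/Provider collaborative (yes/no). Recode it from the Q5 answers already held and state how many services change code. If none does, record that and stop. If any does, refit the selected LCA and report any service whose class changes before Stage 2 sampling, or, if sites are already chosen, before that service is treated as an example of its model.

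The cost is one line of recoding, no new data and at most one refit. The only downside is that a few services could change class.

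For Q9, no correction is called for. At most, give the reason for the grouping and check, as a sensitivity analysis, whether splitting off the no-adult-service answer or placing it by Q8 changes the classes.
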